13.0 Statistical Data Management

Primary data for the exposure group (e.g. the Carevix[™] group) will be collected via Aspivix's secure server. Aspivix has agreed in the Ambassador Agreement to allow access to their data. In the provider section of the survey will be a link to select location site and these data will be separately accessible. The surveys for the patient and provider are connected within the same survey. The data for the control group (e.g. the tenaculum group) will be collected and stored via RedCap, using similar questions to the exposure survey. Aspivix will also furnish us with raw data that will allow us to correlate the date and time of the submitted survey with the date and time of the patient's consented information. This data will be documented in RedCap for the purpose of data analysis. The signed consent forms will be stored in a secure and lockable cabinet.

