4.0 Eligibility Criteria

4.1 Inclusion Criteria (to be assessed prior to procedure)

- Age 18 years or older
- Speaks and reads in English
- Able to consent on their own
- Will undergo any intrauterine procedure using the Carevix[™] (for exposure group) or using Tenaculum (for Control Group)
- Up to 20 providers performing this procedure
- Provider is willing to use Carevix[™] for scheduled procedure

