7.0 Study Procedures

Any intrauterine procedure already scheduled will otherwise proceed accordingly as part of clinical care. During the enrollment, patients who fit above inclusion criteria and are scheduled for an intrauterine procedure may be offered the opportunity to participate in this program and trial the new Carevix[™] device during the exposure recruitment period and complete a short survey. If the patient consents to the use of Carevix[™] Ambassador program, the suction-based cervical stabilizer will be used on their cervix to stabilize the cervix during the procedure instead of the traditional tenaculum. If the patient or provider opts out of the use of Carevix[™], they will be asked if they'd like to participate in the study with the tenaculum. During the tenaculum enrollment phase, patients will receive the standard of care device and complete a short survey.

Following completion of the procedure, the patient will then fill out the patient-based survey. Following the completion of the patient's questions, the provider will then fill out the provider-based survey.

The questionnaire for the Carevix[™] Ambassador program will be stored within the Aspivix company database (all questions are HIPAA compliant and do not reveal PHI). The survey is labeled as originating from Indiana University for easy access to only our patient data.

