14.0 Privacy/Confidentiality Issues

None of the questions on the data collection questionnaire will contain PHI. Data will be stored within the company Aspivix's secure server and on RedCap.

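### Carevix-arm surveys are tied to participants by matching times, with no patient-level key described; a study number on the survey would be a cheap and safer link.

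*Combined protocol and SAP*

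**What the plan says.** Section 13.0 describes two routes for the outcome data. Carevix-arm data "will be collected via Aspivix's secure server". Control data "will be collected and stored via RedCap, using similar questions to the exposure survey".

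For the Carevix arm, the same section says the manufacturer will send raw data that let the site "correlate the date and time of the submitted survey with the date and time" of the patient's consent information, and the result is then recorded in REDCap. The patient and provider parts form one survey.

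The only filter described on the manufacturer's records is the site. Section 7.0 says "The survey is labeled as originating from Indiana University for easy access to only our patient data", and section 13.0 adds: "In the provider section of the survey will be a link to select location site and these data will be separately accessible". Section 14.0 states: "None of the questions on the data collection questionnaire will contain PHI".

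Sections 4.3 and 11.0 provide that a consented patient who turns out to need no cervical stabilization is ineligible and need not complete a survey. Section 11.0 extends this to a patient consented to Carevix whom the provider finds unsuitable for the device, unless she is taken into the tenaculum group.

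The documents give no matching window, no rule for ambiguous, duplicate or unmatched surveys, and no reconciliation of surveys against consents.

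**The concern.** The two times being matched belong to different events. Consent is given before the procedure. The survey is submitted after the procedure, once the patient and then the provider have finished. The interval is not specified and will vary with the procedure and the clinic's flow, so the order of consents on a busy day need not be the order of submissions.

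Consents and surveys are also not one-to-one. If two patients consent on the same morning and one proves to need no stabilization, the single survey that follows could fit either consent. Section 4.1 allows "Up to 20 providers performing this procedure". That line says nothing about linkage, but it makes overlapping sessions plausible.

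Three things depend on the link: which surveys count among the 30 Carevix participants, whether each came from a consented and eligible patient, and which procedure, provider and baseline data go with each pain score. The step is described for the Carevix arm only, so any error from it would fall on one side of the comparison. A link not recorded at the time may be hard to recover later.

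**Working it through.** **1. Is there another key?** Read together, sections 7.0, 13.0 and 14.0 give a server, a site label, a site selection by the provider, no PHI, and a time match. None mentions a study number. That is an inference from silence, because the questionnaire (Attachment #2) is not reproduced. It is a strong inference: a study number on the record would make time matching unnecessary.

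**2. Which linkage errors can reach the planned analysis?** Section 12.0 plans chi-square tests, t-tests and similar standard tests between the groups.
- *Swap between two Carevix participants.* The set of 30 values is unchanged, so its mean, standard deviation and test statistic are unchanged. In a simulated check with 30 values per arm, permuting one arm left the t-test p-value at 0.00198 both times. Pain and bleeding also stay paired, since they sit in one survey. Only analyses that join outcomes to patient-level data, such as by procedure or provider, are harmed.
- *Survey wrongly excluded or wrongly included.* The set of values changes, so the primary comparison can change.

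**3. How often might patients share a day?** The documents give no clinic-day count. Assume 125 clinic days for each of the two six-month phases in section 15.0, and accrual in the order of section 6.0: 25 Carevix patients first, then 5 alongside the controls. With n patients spread evenly at random over D days, the chance that a given patient shares a day with another is 1 − (1 − 1/D)^(n−1).
- First phase, n = 25, D = 125: 1 − (124/125)^24 = 0.175, and 25 × 0.175 = 4.38 patients.
- Second phase, n = 5, D = 125: 1 − (124/125)^4 = 0.032, and 5 × 0.032 = 0.16 patients.
- Total: 4.54 of 30, or 15%.

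Other assumptions raise the figure:

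| Clinic days, phase 1 / phase 2 | Patients sharing a day | Share of 30 |
|---|---|---|
| 125 / 125 | 4.5 | 15% |
| 63 / 125 (first phase three months, the lower end in section 5.0) | 8.0 + 0.16 = 8.1 | 27% |
| 52 / 52 (two procedure days a week, assumed) | 9.3 + 0.37 = 9.7 | 32% |

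These are same-day coincidences, not errors. The match uses time as well as date, so some would be resolved.

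**4. What would wrong exclusion or inclusion do?** Section 12.0 gives 30 per group for at least 80% power at two-sided 5%, but no effect size or standard deviation, so that figure cannot be reproduced. Taking it as exactly 80% power, the implied standardized difference is (1.960 + 0.842) × √(2/30) = 0.72 by the normal approximation. All counts below are assumed.
- *Carevix surveys lost:* power is Φ(0.723/√(1/30 + 1/(30 − k)) − 1.960). For k = 1, 3 and 6 this is 79%, 78% and 75%.
- *Ineligible or non-study surveys among the 30:* if k of them differ in mean pain by s SD, the arm mean moves by k·s/30 SD. For k = 3 and s = 0.5 to 1, that is 0.05 to 0.10 SD; if toward the null, power is 74% to 68%. For k = 6 it is 0.10 to 0.20 SD and 68% to 53%. A shift the other way would exaggerate the difference instead.

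**The case against.** The strongest reply is that the planned comparison largely does not need the link. Section 12.0 names no covariate adjustment and no subgroups, so swaps leave the result as it was. That stands, and it removes the most obvious form of the harm. A reader might infer from the mislinking risk that the primary result would be corrupted; for swaps, it would not be.

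A reader might also infer that surveys from women outside the study will be counted. The documents do not show this. In section 7.0 the device is used when the patient consents, and those who opt out are asked about taking part with the tenaculum; section 11.0 gives decliners standard care. No Carevix use outside consent is described. It remains possible, because the survey belongs to the manufacturer's general program and the filter is by site.

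Nor does an unmatched survey vanish: it stays on the server under the site label. Section 10.0 provides at least monthly review of data quality, recruitment and consent, so a mismatch could be noticed while recent. Both points soften the risk. The review, however, has no stated key to check against, and section 10.0 refers to a Qualtrics database that sections 7.0, 13.0 and 14.0 do not mention.

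Finally, the absence of a study number is inferred, and the documents do not say what identifier the REDCap control records carry. Both caveats stand, and they are a reason to apply the fix to both arms.

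**Conclusion.** The concern holds in limited form. Section 13.0 states a linkage method for the Carevix arm that can be ambiguous when patients are seen close together, and the site label cannot confirm that a survey belongs to a consented, eligible participant. Wrong inclusion, exclusion or mislinking is therefore possible in the one arm for which the step is described.

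The size of the problem is unknown. About 15% of Carevix patients sharing a day, under even accrual over two 125-day phases, indicates the opportunity for ambiguity and is not an error rate. The power figures show only what a given number of lost or misplaced surveys would do, if 30 per group gives exactly 80% power.

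The conclusion rests on no patient-level identifier being on the survey, which the documents imply but do not state. This is a cheap improvement to the plan, not a flaw that invalidates the comparison.

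**What to change.** In section 13.0, replace time matching as the primary key with a sequential, non-PHI study number assigned at consent and entered on the survey in both arms. If the manufacturer cannot add a field, have staff log the exact submission time against the study number at the moment of submission. This still uses time, but it matches submission to submission instead of submission to consent.

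Add three rules:
1. Reconcile surveys against the consent log at the monthly review in section 10.0, accounting for consented patients who completed no survey.
2. Analyse only surveys matched to a logged number.
3. Report the number of unmatched surveys by arm.

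At the same time, make the database named in section 10.0 agree with those in sections 7.0, 13.0 and 14.0, so that it is clear which records the review covers.

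The cost is one extra entry per patient, with no extra visit and no PHI. The downside is some dependence on the manufacturer to add a field, which the log entry covers.

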14.0 Privacy/Confidentiality Issues

None of the questions on the data collection questionnaire will contain PHI. Data will be stored within the company Aspivix's secure server and on RedCap.

15.0 Follow-up and Record Retention

The study will last about 1 year (6 months for Carevix[™] exposure group and approximately 6 months for the control group (e.g. tenaculum). The record retention will be indefinite.

17.0 Appendix

Attachment #1: Carevix[™] data published in the journal *Contraception*. Attachment #2: Questionnaire for patients and providers (done through the same link). Attachment #3: Study information sheet and consent form.
